5.0 STUDY TREATMENT

5.1 Regimens, Administration, and Duration

After a 2-week pravastatin 40mg daily run-in period, subjects will be randomly assigned to rosuvastatin 20mg daily or pravastatin 40mg daily at week 2 in a 1:1 ratio. At week 6, subjects on the Rosuvastatin arm may have their dose escalated to 40mg daily.

Run-in: Pravastatin 40mg daily for 2 weeks (Weeks 0-2)

Randomization (1:1 ratio) at Week 2:

- Moderate intensity strategy: Pravastatin 40mg once daily for 12 weeks (Weeks 2-14)
OR
- High-intensity strategy: Rosuvastatin 20mg once daily for 4 weeks (Weeks 2 to 6)
 - Continue Rosuvastatin 20 mg once daily (Weeks 6 to 14) if:
 - AST or ALT between 1.5x and 3x ULN
OR
 - CK between 3x and 10x ULN
OR
 - Grade 1 or 2 toxicity attributable to rosuvastatin is present
 - Escalation of Rosuvastatin to 40 mg daily (Weeks 6 to 14) if:
 - AST, ALT, and CK \leq 1.5x ULN at week 6
AND
 - CK \leq 3x ULN at week 6
AND
 - No grade 1 or greater toxicity attributable to rosuvastatin is present

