7.0 CLINICAL MANAGEMENT ISSUES

7.1 Toxicity Management

Criteria for subject management, dose interruptions, modifications, and discontinuation of study treatment will be mandated only for toxicities attributable to study-provided drugs (pravastatin and rosuvastatin).

The grading system for drug toxicities is the DAIDS Table for Grading the Severity of Adult and Pediatric Adverse Events, Version 2.0, November 2014, located at <http://rsc.tech-res.com/safetyandpharmacovigilance/gradingtables.aspx>.

The lone difference between the grading system for drug toxicities used in this trial and the DAIDS Table is that our protocol has a lower threshold for grading transaminase (AST and ALT) elevations; based on the current ACC/AHA and National Lipid Association Guidelines, we consider elevation of AST or ALT ≥ 3 x ULN as grounds for holding the study drug (and a grade 3 adverse event in this protocol), and CK ≥ 10 x ULN as a grade 3 adverse event and grounds for holding the study drug.

NOTE: The HILLCLIMBER protocol chair must be notified by e-mail regarding toxicities that result in regimen interruption or discontinuation. Email: [contact]. General guidelines presented in sections 7.1.1 to 7.1.3 apply to toxicities that are not specifically discussed further below.

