7.1 Toxicity Management

7.1.1 General Reactions

Grade 1 or 2

Subjects who develop a Grade 1 or 2 toxicity may continue study treatment.

Grade 3

Subjects who develop a Grade 3 toxicity that is judged by the site investigator to be study drug-related should have the study drug held and the study team should be consulted. The subject should be followed closely and if the toxicity does not return to Grade ≤ 2 within 2 weeks, the study drug must be permanently discontinued with subject evaluations as per section 6.2.4.

If the study drug is resumed and the same Grade 3 toxicity recurs within 4 weeks of reintroduction, and the site investigator considers this AE related to the study drug, the drug must be permanently discontinued.

With a Grade 3 toxicity that is judged not related to the study drug by the site investigator, the study drug may be continued at the discretion of the site investigator in consultation with the study team.

Grade 4

Subjects who develop a Grade 4 toxicity will have the study drug permanently discontinued, with clinical assessments and laboratory testing as described for Grade 3 toxicity. If the investigator feels that the toxicity is clearly related to another cause and that the toxicity is not caused by the study drug, and after consultation with the study team, dosing may continue when the toxicity has resolved to Grade 2 or less.

Subjects experiencing Grade 4 toxicities should be followed closely with additional clinical assessments and laboratory testing as clinically indicated in consultation with the study team.

NOTE: Direct and indirect bilirubin elevations that reach Grade 4 elevations according to the DAIDS toxicity schema and are related to atazanavir are excluded from reporting.

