7.1.3 Myalgias and Myopathy

Persons who present with significant myalgias (Grade ≥ 3 , ie, muscle pain causing inability to perform usual social and functional activities) should be evaluated with a clinical assessment that includes an evaluation of CK, serum creatinine, potassium, and urinalysis. Myopathy is defined as muscle aches, soreness, tenderness, or weakness with creatinine kinase (CK) $>10 \times$ ULN not related to exercise or other causes, including trauma. If the symptoms are associated with Grade ≥ 3 elevation in CK ($10 \times$ ULN) (see table below) that is not related to exercise or other cause, study medications should be permanently discontinued. Subjects will be followed on study, off treatment through the study termination visit with subject evaluations as per section 6.2.4.

NOTE: Mitochondrial toxicity related to nucleoside therapy and not related to study medication is a possibility, and evaluations for lactic acidosis should be considered by the subject's primary care provider.

Serum CK Toxicity Grading*

Toxicity Grade	Value
Grade 1	$3 - <6 \times$ ULN
Grade 2	$6 - <10 \times$ ULN
Grade 3	$10 - <20 \times$ ULN
Grade 4	$\geq 20 \times$ ULN

* Not related to exercise or other cause

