9.5 Monitoring

When approximately 50% of patients have completed the study through week 6, an interim analysis for safety will be conducted by an independent data monitoring committee. Patients with levels of CK, AST, ALT at weeks 2, 6, or 10 that are 3 times the upper limit of normal or greater will have the study drug discontinued at that time. If >25% of study enrollees are required to have the study drug discontinued at the interim analysis, the trial will be stopped. Serious adverse events will be monitored by the committee on an ongoing basis throughout the study. If a study patient has CK, AST, or ALT levels of 3 times the upper limit of normal or greater any time prior to the interim safety analysis, the study coordinator will alert the medical safety officer ([name]), who will contact the patient and instruct the patient to immediately discontinue the study drug. Such patients who discontinue the study drug at the

medical safety officer's request will continue to be followed in the study and included in intention-to-treat analyses.

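### For CK of 3 to <10x ULN, section 9.5 stops study drug and counts the stop toward ending the trial, sections 5.1 and 7.1 let drug continue, and nothing says which governs

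*Combined protocol and SAP*

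**What the plan says.** Section 9.5 (Monitoring) applies one limit to three laboratory tests. "Patients with levels of CK, AST, ALT at weeks 2, 6, or 10 that are 3 times the upper limit of normal or greater" are to have study drug discontinued. For a value of "3 times the upper limit of normal or greater any time prior to the interim safety analysis", the medical safety officer tells the patient to stop at once. The trial-level rule follows from this: "If >25% of study enrollees are required to have the study drug discontinued at the interim analysis, the trial will be stopped".

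Other sections treat CK differently.

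- Section 5.1, rosuvastatin arm at week 6: "CK between 3x and 10x ULN" is one of the conditions for staying on 20 mg through week 14.
- Section 7.1: CK at or above "10 x ULN as a grade 3 adverse event and grounds for holding the study drug". Management actions are "mandated only for toxicities attributable to study-provided drugs".
- Section 7.1.3, in the table headed "Serum CK Toxicity Grading": 3 to <6x ULN is Grade 1, 6 to <10x is Grade 2, and Grade 3 starts at 10x.
- Section 7.1.1: "Subjects who develop a Grade 1 or 2 toxicity may continue study treatment".

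Section 9.2.1 lists discontinuation for adverse events and CK above 3x ULN among the safety endpoints. After entry, section 6.3.5 requires a CK value on the CRF only if it is Grade 2 or higher or leads to a treatment change. Lipids, creatinine and liver tests are recorded at any grade.

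**The concern.** The same CK result leads to different actions depending on which section the site has open. Three things then depend on that choice: whether the patient stays on drug, whether the patient adds to the 9.2.1 discontinuation endpoint, and whether the patient counts toward the 25% rule on which the data monitoring committee would end the trial. Section 9.5 keeps such patients in the intention-to-treat analysis, so the choice also affects how many week 14 LDL-c values are measured off drug. A stopping rule should give one answer for one set of laboratory results, and this one does not.

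**Working it through.** The plan gives no operating figure for the stopping rule, so there is nothing of its own to reproduce here. The check is a comparison of the rules, followed by a bounded illustration.

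**Step 1. One result under each rule.** Take a CK of 5x ULN.

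| Setting | 9.5 | 5.1 | 7.1, 7.1.1, 7.1.3 |
|---|---|---|---|
| Rosuvastatin, week 6 | Stop; counts toward 25% | Continue 20 mg | Grade 1; may continue |
| Rosuvastatin, week 10 | Stop | No rule | Grade 1; may continue |
| Pravastatin, weeks 2, 6 or 10 | Stop | No rule | Grade 1; may continue |

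In the first row, 5.1 and 9.5 cannot both be followed. In the other rows a site can satisfy both by stopping, but a site that works from section 7 would have no reason to.

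**Step 2. Is there a precedence rule?** Section 8.1 refers toxicity discontinuation to section 7.0; it neither mentions nor overrides 9.5. The note in 7.1 orders the general guidelines against specific toxicities and is also silent on 9.5. No other section ranks the rules.

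**Step 3. Does attribution resolve it?** Section 7.1 limits its mandates to attributable toxicity, and 9.5 has no such condition. Reading that condition into 9.5 does not help: an attributable CK of 5x is still stopped by 9.5 and continued by 5.1.

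**Step 4. Recording.** A CK of 3 to <6x is Grade 1. If the site follows 9.5, treatment changes and 6.3.5 requires the value on the CRF. If it follows 5.1 or 7.1, treatment does not change and the CRF entry is not required. Section 6.3 still requires the value in source documents.

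**Step 5. The stopping count.** The smallest count above 25% of n is r = floor(0.25n) + 1. Section 9.5 places the interim at about half of patients through week 6, but sets the percentage against enrollees. The synopsis gives 40 subjects; section 9.4 gives 30, with up to 50.

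- Half enrolled as denominator: 4 of 15, 6 of 20, 7 of 25.
- All enrolled as denominator: 8 of 30, 11 of 40, 13 of 50.

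**Step 6. Illustration with assumed rates.** The documents give no frequency for CK of 3 to <10x, nor for laboratory stops. (The 5-20% in 9.4 is for symptoms on statins.) Assume that 5% stop under either rule and that a further q have CK of 3 to <10x. The chance of ending the trial is P(Bin(n, p) ≥ r), with p = 0.05 if those CK values do not count and p = 0.05 + q if they do.

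| n (r) | Not counted | q = 5% | q = 10% | q = 15% | q = 20% |
|---|---|---|---|---|---|
| 15 (4) | 0.55% | 5.6% | 17.7% | 35.2% | 53.9% |
| 20 (6) | 0.03% | 1.1% | 6.7% | 19.6% | 38.3% |
| 25 (7) | 0.02% | 0.95% | 7.0% | 22.0% | 43.9% |

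The range runs from negligible to large, and nothing in the documents says where in it the trial lies.

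**The case against.** The strongest reply is that section 7 only permits continuation and calls CK of 10x grounds for holding, without saying that drug may be held for CK only there. A stricter mandate in 9.5 can sit beside a permission, and 8.1 points to section 7.0 for toxicity stops. This has force for pravastatin patients and for rosuvastatin patients outside week 6, where the text is unclear rather than contradictory. It does not reach week 6 on rosuvastatin, where 5.1 sets continuation of 20 mg as the action.

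A second reply is that the effect on the trial-level rule has not been shown. That stands. At n = 20, if 5% had CK in this range and nobody else stopped, the chance of six or more is 0.03%; at 10% it is 1.1%.

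A third is that CK data are not lost, because source documents hold them. That also stands; the gap is in CRF entry only.

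A reader might also infer two further faults in 5.1. The first is that its escalation limits for CK, 1.5x in one line and 3x in another, conflict. They are joined by AND, so the stricter one applies and the other is redundant. The second is that CK above 1.5x and below 3x has no instruction. Section 5.1.1 makes week 6 a choice between two tablets and one, so a patient who fails an escalation criterion stays on one.

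**Conclusion.** The inconsistency is in the current text and does not depend on any assumed rate. For CK of 3 to <10x ULN it is a direct contradiction for rosuvastatin at week 6, and a mandate against a permission in the other settings. It reaches individual treatment, a safety endpoint and the rule for ending the trial. The size of its effect is unknown, and the probabilities above only illustrate a range.

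A reader might go further and infer that entry criterion 4.2.11, which excludes CK only above 10x, lets patients with a stable raised CK inflate the stopping count. The documents do not support giving this weight: they give no prevalence of raised CK at entry, and the attribution condition in 7.1 leaves the reading open to dispute. Nor do they support saying that the trial is likely to be stopped wrongly. The point should be corrected before the interim analysis.

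**What to change.** 1. Use one CK limit in 5.1, 7.1 and 9.5. The simplest change is for 9.5 to act on CK at 10x ULN or more, as 5.1, 7.1 and 7.1.3 already do, leaving AST and ALT at 3x. If the clinical team prefers 3x, which is defensible because section 2.1 reports no trials of this dose in this population, remove the 5.1 condition that continues 20 mg at CK between 3x and 10x, and amend 7.1 to match.
2. State that the 25% rule counts discontinuations required under that single limit, and state whether its denominator is all enrolled patients or those through week 6.
3. Amend 6.3.5 so that every post-entry CK is recorded regardless of grade, and report CK above 3x ULN by arm to the committee.
4. Leave the 1.5x CK escalation limit in 5.1 as it is unless the clinical team decides otherwise.

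The cost is a short amendment and slightly more CK data entry. CK is already drawn at every visit, so no test or visit is added. Under the 10x option, CK of 3 to <10x no longer counts automatically toward stopping the trial; the by-arm report in item 3 keeps it in the committee's view.

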7.1.2 ALT and AST elevations

ALT and AST levels will be routinely evaluated at screening, week 0, 2, 6, 10, and 14 visits. All other evaluations of ALT and AST will be performed at the discretion of the site investigator based on subject symptoms.

Grade 3

Subjects who develop *asymptomatic* $>3 \times$ ULN ALT or AST elevations (Grade 3), study drug should be held for 2 weeks and the individual should be re-evaluated 3 weeks after drug discontinuation. If at that time the ALT or AST elevation is $\leq 3 \times$ ULN and subjects remain asymptomatic, the subjects are eligible to continue on study treatment at the discretion of the site investigator. If the ALT and AST are not $\leq 3 \times$ ULN within the 2 week period, the study drug must be permanently discontinued unless the ALT and AST elevations are deemed not related to study drug upon further assessment as per the discretion of the care provider (ie, acute hepatitis A or other clear causation).

For any *symptomatic* (eg, fatigue, nausea and vomiting, right upper quadrant pain, rash or eosinophilia) ALT or AST $>3 \times$ ULN (Grade 3), study drug should be held. Subjects should be asked to return to the research site for repeat testing 2 weeks later. If repeat ALT and AST is $\leq 3 \times$ ULN and the subject is no longer symptomatic, study drug can be resumed.

Grade 4

For any ALT or AST $>6 \times$ ULN (Grade 4), the study drug should be discontinued. The subject should be brought back for repeat testing every 1 week until the ALT and AST $\leq 3 \times$ ULN. Even if ALT and AST are $\leq 3 \times$ ULN upon repeat testing for these patients, the study drug will not be restarted at that time.

NOTE: If the Grade 3 or 4 elevation is clearly related to another cause and not related to study drug (eg, acute hepatitis A infection), the subject should be brought back for repeat testing every 2 weeks for Grade 3 or every 1 week for Grade 4 until the ALT or AST $\leq 3 \times$ ULN. The local site investigators should contact the study team for approval before resuming study drug. Subjects who permanently discontinue study drug will be followed on study, off treatment through the study termination visit with subject evaluations as per section 6.2.4.

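### For AST/ALT from 3x to 6x ULN, Section 9.5 has study drug discontinued with no restart path, while Sections 7.1 and 7.1.2 set a hold with recheck and possible restart, and nothing says which governs

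*Combined protocol and SAP*

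**What the plan says.** **Section 9.5 (Monitoring).** Patients with CK, AST or ALT at weeks 2, 6 or 10 that is "3 times the upper limit of normal or greater will have the study drug discontinued at that time". For such a value at any time before the interim safety analysis, the coordinator alerts the medical safety officer, "who will contact the patient and instruct the patient to immediately discontinue the study drug". Patients who stop at the "medical safety officer's request will continue to be followed in the study and included in intention-to-treat analyses". The same section stops the trial if more than 25% of enrollees are required to have study drug discontinued.

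**Section 7.1 (Toxicity Management).** On transaminases: "we consider elevation of AST or ALT ≥ 3 x ULN as grounds for holding the study drug". The protocol grades this as 3.

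**Section 7.1.2 (ALT and AST elevations).** This covers the same scheduled tests.
- Asymptomatic Grade 3: drug is held for 2 weeks and the patient is re-evaluated at 3 weeks. If the value is then no more than 3x ULN and there are still no symptoms, "the subjects are eligible to continue on study treatment at the discretion of the site investigator".
- Symptomatic Grade 3: drug is held and the test repeated 2 weeks later. If the value is no more than 3x ULN and "the subject is no longer symptomatic, study drug can be resumed".
- Above 6x ULN (Grade 4): drug is discontinued, and a separate sentence rules out restarting it then.
- Elevations clearly due to another cause have their own path.

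**The concern.** A patient with AST or ALT between 3x and 6x ULN falls under both sets of instructions, and they lead to different drug exposure. The primary analysis (Section 9.6.1) uses only the week-2 and week-14 LDL-c. Patients taken off drug stay in the intention-to-treat analysis, so the section that is followed helps decide whether a recovered patient is on or off statin when the week-14 sample is drawn. Keeping the patient in the analysis does not settle which exposure that sample reflects.

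The same choice affects three counts: adverse-event-related discontinuation in the safety endpoints of Section 9.2.1, time to discontinuation in Section 9.6.2, and possibly the 25% stopping rule in Section 9.5. The plan does not say whether a hold followed by restart is a discontinuation for any of them.

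This point is about transaminases only.

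**Working it through.** **1. The sections side by side, AST/ALT from 3x to 6x ULN**

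| | Section 9.5 | Sections 7.1 and 7.1.2 |
|---|---|---|
| Trigger | 3x ULN or more | 3x or more (7.1); above 3x (7.1.2) |
| Action | discontinue | hold |
| Recheck | none described | 2 weeks (symptomatic) or 3 weeks (asymptomatic) |
| Restart | none described | possible if 3x ULN or less and symptom-free |
| Unrelated cause | no exception | separate path |
| Who acts | medical safety officer (before the interim) | site investigator |

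Above 6x ULN both have drug discontinued, so the conflict is confined to the band from 3x to 6x. Section 9.5 does not refer to Section 7. Section 8.1 ties toxicity-related permanent discontinuation to Section 7, not to 9.5. No section states an order of precedence.

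**2. Exposure at week 14 for a patient who recovers**

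Weeks off drug under 9.5 = 14 − week of finding. Weeks back on drug under 7.1.2 = 14 − (week of finding + 2 or 3).

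- Week 6: 14 − 6 = 8 weeks off; against 14 − 8 = 6 or 14 − 9 = 5 weeks back on.
- Week 10: 14 − 10 = 4 weeks off; against 14 − 12 = 2 or 14 − 13 = 1 week back on.
- Week 2: this coincides with randomization, and significant toxicity then bars randomization (Section 3.0). The effect is mainly on who is randomized.

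**3. The plan's own figure**

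Section 9.4 uses a difference of 25 mg/dl, SD 20, power 0.80 and two-sided alpha 0.05. Then n = 2 × [20 × (1.960 + 0.842) / 25]² = 10.05, rounded up to 11 per arm. This matches the plan and is not in dispute.

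**4. Upper-bound size for one patient**

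Inputs from Section 9.4: mean LDL-c about 105 mg/dl for participants, 75 expected on pravastatin, 50 on rosuvastatin. Assumptions that the plan does not make: LDL-c is 75 at week 2, returns fully to 105 off drug, and returns fully to the expected on-drug level after restart.

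- Off drug at week 14: (105 − 75)/75 = +40.0%.
- Rosuvastatin resumed: (50 − 75)/75 = −33.3%. Contrast 40.0 + 33.3 = 73.3 points.
- Shift in the arm mean: 73.3/15 = 4.9 points (enrolment goal of 30 in 9.4), or 73.3/20 = 3.7 points (40 subjects in 9.1).
- Pravastatin resumed: (75 − 75)/75 = 0%. Contrast 40 points; 40/15 = 2.7 or 40/20 = 2.0.
- Expected effect on the same scale: 0 − (−33.3) = about 33 points.

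Range: if a restarted rosuvastatin patient gets only halfway back, to (105 + 50)/2 = 77.5 mg/dl, the change is (77.5 − 75)/75 = +3.3%. The contrast is then 36.7 points, or 36.7/15 = 2.4 and 36.7/20 = 1.8 on the arm mean. If the investigator does not restart an asymptomatic patient, both routes leave the patient off drug and the contrast is zero.

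**The case against.** A reader might infer that the two sections cannot both be followed, or that the Grade 3 branch of 7.1.2 can never be used before the interim. The documents do not support that. The protocol writes of permanent discontinuation where it means it (7.1.1, 7.1.2, 7.1.3, 7.1.4). Section 7.1.2 refers to its own two-week hold as a discontinuation of drug. Section 7.2 speaks of treatment stopped temporarily or permanently. For Grade 4, 7.1.2 adds a sentence against restarting, which would be redundant if *discontinued* alone excluded it. Nor does staying in follow-up and in the intention-to-treat analysis imply permanence, since 7.2 follows temporary discontinuers too. So 9.5 can be read as *stop now*, with 7.1.2 governing what comes next. This stands as a possible reading. It does not remove the problem, because 9.5 gives no restart path and no reference to 7.1.2, and staff would have to guess.

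A reader might also infer a material change in the chance of stopping the trial early. That cannot be shown. The 5–20% in 9.4 concerns on-treatment symptoms, not transaminases, and patients above 3x ULN are excluded at entry (4.2.11). Read within 9.5 alone, a patient at 3x ULN may count toward the 25% whether or not drug is resumed.

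Nor do the documents show that staff would pick the section case by case. Before the interim the medical safety officer acts, and 7.1 requires interruptions and discontinuations to be reported to the protocol chair.

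Finally, 73 points is a ceiling. It is least plausible after a week-10 finding, which leaves only 1 to 2 weeks back on drug.

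**Conclusion.** The inconsistency is real, is in current text, and should be resolved. For AST/ALT from 3x to 6x ULN, 9.5 states discontinuation and is silent on what follows, while 7.1 and 7.1.2 state a hold with possible restart. Nothing decides between them. It is best described as an unreconciled instruction that can be read two ways, not as an outright impossibility.

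The firm part of its size is exposure: at week 14, 8 weeks off against 5 to 6 weeks back on after a week-6 finding, and 4 off against 1 to 2 back on after a week-10 finding. This rests on the plain reading of 9.5, on recovery, and on restart at the recheck. The LDL-c contrast for one rosuvastatin patient runs from zero to 73 points, or up to 4.9 points on a 15-patient arm mean and 3.7 on a 20-patient arm mean. The upper end rests on the assumed full returns to 105 and 50 mg/dl. How many patients would be affected, and what that would do to the stopping rule, cannot be estimated from the plan.

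Safety is listed as a primary endpoint in 9.2.1 but as secondary in 1.2 and 9.2.2. The ambiguity over what counts as a discontinuation therefore touches a safety endpoint whose rank is itself unsettled.

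**What to change.** Reconcile 9.5 with 7.1, 7.1.1 and 7.1.2 so that one AST/ALT action applies from 3x to 6x ULN. Give one statement on restart and one on unrelated causes, and have 9.5 refer to it. Which rule stands is for the clinical team. In the same edit, settle two smaller differences: the trigger (3x or more against above 3x), and the timing in 7.1.2, where drug is held for 2 weeks, re-evaluation is at 3 weeks, and failure to recover is judged within 2 weeks.

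Then state whether a hold followed by restart counts as a discontinuation in each of:
- the safety endpoint in 9.2.1;
- the time-to-discontinuation summary in 9.6.2;
- the 25% stopping rule in 9.5.

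The cost is a short wording amendment, with no added visits, tests or patients.

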3.0 STUDY DESIGN

This is a single center, randomized, controlled, open-label phase II trial. Up to 40 subjects not already on high dose statin therapy who have documented CHD and/or calculated 10-year ASCVD risk >15% will be included and started on moderate dose statin therapy (pravastatin 40mg daily) for an initial two-week run-in period. Subjects not demonstrating significant toxicity at week 2 will then be randomized to rosuvastatin 20mg versus continuing pravastatin 40mg daily. Subjects will return at week 6; those in the rosuvastatin arm who do not demonstrate significant safety or toxicity concerns will then have doses increased to rosuvastatin 40mg (high dose group). The group randomized to pravastatin 40mg daily at week 2 will not have their dose increased at the end of week 6.

The following treatment regimens will be used:

Stage One (Run-in): Pravastatin 40mg daily (Weeks 0-2),

Stage Two (Randomization in 1:1 ratio):

- Moderate intensity group: Pravastatin 40mg daily (Weeks 2-14)
OR
- High intensity group: Rosuvastatin 20mg daily (Weeks 2-6), potentially titrated to Rosuvastatin 40mg daily (Weeks 6-14).

Total duration of the study is 14 weeks: 2 weeks for the initial run-in, 6 weeks following randomization, and 6 weeks following dose increase.

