9.3 Randomization and Stratification

Subjects who meet enrollment criteria will be randomized at Week 2 in a 1:1 ratio according to the study treatment that has been randomly assigned to the Patient Number on the Randomization List held by the local site pharmacist. Randomization will be stratified by: (1) type of ART: patients taking any booster (ritonavir or cobicistat) as part of their ART regimen and patients not taking a booster; and (2) known CHD or not.

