9.4 Sample size and Accrual

The predicted percent reduction in LDL-c by rosuvastatin dose is as follows: 20mg (55-60%), and 40mg (60-63%). The predicted percent reduction in LDL-c by pravastatin 40mg is 30%. The expected difference in LDL-c for subjects receiving high (rosuvastatin 20-40mg daily) versus moderate (pravastatin 40mg daily) intensity statin doses in this study is therefore approximately 25-30% compared with moderate. In a landmark study of patients with CHD comparing high intensity statin (atorvastatin 80mg, which is similar in intensity of expected lipid lowering to rosuvastatin 20-40mg) versus pravastatin 40mg, mean LDL cholesterol levels during treatment were 62mg/dl and 95mg/dl for high intensity and pravastatin groups (with standard deviations of approximately 20mg/dl), respectively.

Given potentially lower baseline LDL cholesterol levels in this study (we expect mean LDL of participants will be approximately 105, including patients off statin therapy and those on low intensity therapy), realistic expected mean LDL cholesterol levels are 75mg/dl for the pravastatin group and 50mg/dl for the high-intensity/rosuvastatin group. These expected LDL cholesterol levels are similar to those seen in the high intensity versus lower intensity treatment groups in a more recent trial of lipid-lowering strategies in high-risk patients, in which there was no excess of adverse events in the higher-intensity group which achieved a mean LDL of 53.7mg. In order to have a power of 0.80 with a two-sided alpha of 0.05 to detect a 25mg/dl difference in LDL-c lowering with a standard deviation of LDL-c of 20, the desired sample size would be at least 11 cases and 11 controls. Given the potential for study drug discontinuation in an expected 8 or fewer patients (based on on-treatment symptoms being present in 5-20% of patients on statins), the goal subject enrollment for this study is 30 with a possible enrollment of up to 50 participants in order to ensure adequate power.

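### The only numeric safety stopping rule pools both arms over an undefined denominator, so it is insensitive to toxicity confined to rosuvastatin

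*Combined protocol and SAP*

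**What the plan says.** Section 9.5 (Monitoring) plans a single interim safety analysis by an independent committee, timed thus: "When approximately 50% of patients have completed the study through week 6". The stopping rule is: "If >25% of study enrollees are required to have the study drug discontinued at the interim analysis, the trial will be stopped". The events that force a patient off drug are described as "Patients with levels of CK, AST, ALT at weeks 2, 6, or 10 that are 3 times the upper limit of normal or greater".

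Section 9.3 places randomisation at the week-2 visit: "Subjects who meet enrollment criteria will be randomized at Week 2 in a 1:1 ratio". A week-2 laboratory event is therefore a pravastatin run-in event.

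The planned size is not stable. Section 3.0 has "Up to 40 subjects not already on high dose statin therapy", and the synopsis and Section 9.1 also give 40, but Section 9.4 says "the goal subject enrollment for this study is 30 with a possible enrollment of up to 50 participants".

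Section 9.5 also has the committee follow serious adverse events throughout, with no numeric or by-arm boundary. It states no operating characteristics for the 25% rule.

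**The concern.** The safety uncertainty in this trial lies mainly in one arm. Sections 2.0 and 2.1 say that high-intensity rosuvastatin has not been studied in people with HIV on antiretroviral therapy, whereas every participant takes pravastatin 40 mg in the run-in and half stay on it. If toxicity is confined to rosuvastatin, a pooled percentage roughly halves the signal before it meets the threshold. A wider count of enrollees can dilute it further with patients still in run-in or without week-6 results, and week-2 events add counts that say nothing about rosuvastatin. At stake is whether a high rate of forced discontinuation on rosuvastatin would prompt a decision about the trial as a whole, or would only lead to patients being taken off drug one at a time.

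**Working it through.** **The plan's own figure.** There is none for this rule. The sample size in Section 9.4 (11 per arm for a 25 mg/dl difference, SD 20) reproduces: the t-based solution is 11.09, and power at 11 per arm is 0.796. It has no bearing on the stopping rule.

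**Inputs from the documents.** Threshold above 25%; look at about half the patients through week 6; 1:1 allocation; planned size 40, or 30 with up to 50.

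**Assumed inputs.** True rates of required discontinuation: rosuvastatin 30 to 60%, pravastatin 0 to 10%. The only related figure in the documents is 5-20% for on-treatment symptoms (Section 9.4), which is a different event.

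**Step 1: count needed.** With denominator D, the smallest count above 25% is k = floor(0.25 × D) + 1.
- D = 20 (half of 40): k = 5 + 1 = 6.
- D = 15 (half of 30): 0.25 × 15 = 3.75, so k = 3 + 1 = 4.

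With 10 per arm, 5 rosuvastatin events and none on pravastatin give 5/20 = 25% exactly, which is not above 25%.

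**Step 2: chance of stopping.** With X events on rosuvastatin and Y on pravastatin, independent binomials, P(stop) = Σ P(Y = j) × P(X ≥ k − j). At 40%/5%, 10 per arm and k = 6:

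0.5987 × 0.1662 + 0.3151 × 0.3669 + 0.0746 × 0.6177 + 0.0105 × 0.8327 + 0.0010 × 0.9536 = 0.271.

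| True rosuvastatin rate | N = 40, 10 vs 10, k = 6; pravastatin 0% / 5% / 10% | N = 30, 8 vs 7, k = 4; pravastatin 0% / 5% |
|---|---|---|
| 30% | 5% / 11% / 19% | 19% / 28% |
| 40% | 17% / 27% / 38% | 41% / 50% |
| 50% | 38% / 49% / 60% | 64% / 71% |
| 60% | 63% / 72% / 80% | 83% / 87% |

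The N = 30 column puts the odd patient on rosuvastatin. If the split is 7 vs 8, the 40%/5% and 50%/5% figures fall to 40% and 60%.

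**Step 3: a wider denominator.** Suppose 30 are enrolled when 20 have reached week 6. Then 0.25 × 30 = 7.5 and k = 8. At 40%/5% the chance of stopping is:
- 4% if the extra 10 patients contribute no events;
- 9% if each has a 5% chance of an event;
- 35% if they are already randomised 5 and 5 and have had the full 40%/5% risk.

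A wider denominator therefore lowers sensitivity unless the added patients have had about the same opportunity for events as those through week 6.

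**Step 4: the same 25% within the rosuvastatin arm.** With 10 patients, k = floor(2.5) + 1 = 3. P(3 or more of 10) is 83% at a true 40%, 32% at 20%, 7% at 10% and 1% at 5%. With 8 patients (3 needed) it is 69% at 40% and 20% at 20%.

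**Step 5: false alarms.** When both arms share one rate there is no rosuvastatin-specific harm. At 20% in both arms (10 each) the pooled rule fires 20% of the time and the arm-specific cut 32%. At 10% in both, the figures are 1% and 7%.

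**The case against.** The case on the other side has several parts.

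- **The denominator is open.** A reader might infer that it certainly includes run-in patients and those without week-6 results, and so quote very low chances of stopping. Section 9.5 does not settle this. The rule follows closely on the sentence that times the look by patients through week 6, so enrollees may mean that group. The 4% figure in Step 3 also depends on the extra patients having no events. This part of the objection stands, which is why the main results use the favourable reading.
- **The rule is not inert.** A reader might infer that severe rosuvastatin toxicity would usually be missed. That depends on the rate and the trial size. With 20 at the look the rule fires 72% of the time at 60%/5%, and with 15 at the look about half the time at 40%/5%. This also stands.
- **The purpose is not stated.** Nothing says the rule exists to detect harm specific to rosuvastatin. It can be read as an overall tolerability stop in a pilot, since Section 2.0 leaves adequately powered safety evaluation to later trials. This stands too, and it is a reason to keep the pooled rule.
- **Other safeguards exist.** Patients at 3 times the upper limit are taken off drug under Section 9.5, Section 7.1 has toxicity rules, week-6 escalation is conditional, the committee follows serious adverse events, and the trial is open-label. These protect individuals and allow judgement. None supplies a by-arm threshold for the trial, and a laboratory rise that forces discontinuation need not be a serious adverse event.
- **An arm-specific cut raises more alarms.** Step 5 confirms it. Comparing 83% with 27% also sets a review trigger against automatic closure, so it is not a like-for-like gain in stopping power.

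**Conclusion.** The point holds as a limitation of the rule's sensitivity. On a favourable reading at 40 patients, half the rosuvastatin arm can be forced off drug with no pravastatin events and the trial continues. With pravastatin at 5%, the chance of stopping reaches about one half only when the true rosuvastatin rate is about 50%; at the goal of 30 patients it does so at about 40%. Above those rates the rule more often fires than not on this reading.

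The size rests on assumed discontinuation rates, independent events, near-equal arms at the look, and a denominator limited to patients through week 6.

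Two conflicts prevent final figures. Section 9.5 discontinues drug at CK of 3 times the upper limit or more, Section 5.1 continues rosuvastatin 20 mg with CK between 3 and 10 times, and Section 7.1 holds drug at 10 times or more; so which events count as required discontinuation is unclear. The planned size is 40 in the synopsis and Sections 3.0 and 9.1, but 30 with up to 50 in Section 9.4. These passages must be reconciled first.

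**What to change.** In Section 9.5:

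1. Define the denominator as randomised patients who have reached week 6, by time on study, so that someone taken off drug earlier still counts.
2. Count required discontinuations after randomisation, by arm, and report run-in events separately.
3. Show both arms to the data monitoring committee.
4. Keep the existing pooled 25% rule. Add more than 25% within the rosuvastatin arm as a trigger for committee review, not automatic closure.
5. State the operating characteristics: with 10 rosuvastatin patients, 3 or more gives 83% at a true 40%, 32% at 20%, 7% at 10% and 1% at 5%.
6. Reconcile the discontinuation thresholds across Sections 5.1, 7.1 and 9.5, and the planned size across the synopsis and Sections 3.0, 9.1 and 9.4; then recompute.

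The cost is a wording change and one by-arm interim table; Section 9.6.2 already plans safety summaries by treatment group. The downside is more committee reviews at small numbers, for example about one look in three at a true 20% rate, which is why the trigger should lead to review only.
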